## 6.6 Safety Analysis

### 6.6.1 Adverse Events

All AEs and SAEs will be coded using Medical Dictionary for Regulatory Activities and will be analyzed in terms of system organ class (SOC) and preferred term (PT). Additionally, solicited AE will be analyzed in terms of systemic AE and local AE, which are predefined in the protocol. This study mainly analyzes Treatment Emergent Adverse Event (TEAE), which occurs after vaccination. The AEs occur before vaccination will only be displayed in the listing. Unless particularly stated, hereinafter all of the AEs are TEAE.

AE will be summarised per phase and immunization schedule as follows: The counts and proportion for AE, related AE, and unrelated AE will be summarised. Fisher exact test will be used to test the difference among groups. Besides, AE and related AE will be analyzed according to the severity, dose distribution, and occurrence time. Related and unrelated AE will be listed, respectively.

AE after every dose will be summarized using the Safety Set for the corresponding dose, respectively. AE occurrence will be compared between immunization schedules by group.

The counts and proportions for SAE, related SAE, and unrelated SAE will be summarised by the group. Fisher exact test will be used to test the difference among groups. SAE will be listed.

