## 3. Design

### 3.1 Overall Design

Single centered, randomized, double-blinded, and placebo-controlled clinical trial design is adopted.

A total of 144 healthy adults aged 18~59 years old are selected as subjects in phase I. After informed consent, subjects who pass the physical examination, meet the inclusion criteria and did not meet the exclusion criteria will be enrolled into the study. The subjects for the emergency immunization schedule (day 0, 14) and routine immunization schedule (day 0, 28) respectively, with 72 subjects for each immunization schedule. Simultaneously, subjects are phased enrolled, with 36 at medium dosage stage which will run-in first, following by 36 at high dosage stage. The subjects enrolled in each dosage stage will be randomly assigned in a 2:1 ratio to receive vaccine or placebo. The high dosage stage vaccination will start only with the condition that safety observation 0~7 days after the first dose of the medium dosage stage vaccination is finished, and the good safety profiles are confirmed by the DMC, according to the occurrence of the solicited and unsolicited adverse events, as well as the occurrence of the abnormal results of the blood routine, blood biochemistry, and urine routine testing.

The phase II clinical trial will start only with the condition that safety observation 0~7 days after the first dose of the high dosage stage vaccination is finished, and the good safety profiles are confirmed by the DMC. A total of 600 healthy adults aged 18~59 years old are selected as subjects. After informed consent, subjects who pass the physical examination, meet the inclusion criteria and didn't meet the exclusion criteria will be enrolled into the study. Subjects will receive two doses of injection at the emergency immunization schedule of day 0,14 or routine immunization schedule of day 0,28, with 300 subjects for each immunization schedule. The subjects for each schedule will be

randomly assigned in a 2:2:1 ratio to receive the medium dosage, high dosage vaccine, or placebo.

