- The safety set is divided into total safety set, first dose safety set, and second dose safety set. The safety analysis of each dose was based on the actual number of vaccinated people. The first dose of safety set includes all subjects who have completed the first dose of vaccination, which are recorded as SS1; the second dose of safety set includes all subjects who have completed the second dose of vaccination and are recorded as SS2.

The above analysis sets will be discussed and decided by the main researcher, the sponsor, the statistician, and the data manager before the database is locked and in the data blind audit process.

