### 6.6.2 Laboratory Test

Laboratory parameters for emergency immunization schedule and routine immunization schedule in Phase I will be analyzed in the following way.

Laboratory parameters at each time point and change from baseline to each post-baseline time point will be summarized using descriptive summary statistics for each parameter by group, and ANOVA will be used to detect the difference among groups. Group t-test will be used to detect the difference between immunization schedules by group.

Additionally, the counts and frequency of laboratory clinical significances will be calculated for each parameter and visit by group. Fisher exact test will be used to detect the difference for each parameter and visit among groups. Shift Tables from pre-vaccination to post-vaccination will be provided for each laboratory parameter by the group.

Also, the occurrence of clinically significant abnormal laboratory results within a trial subject will be analyzed using descriptive summary statistics for each parameter and visit by group.

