#### **6.6.4 Inflammatory Factors**

The statistical method for inflammatory factors evaluation for emergency immunization schedule and routine immunization schedule in Phase I will be carried out as follows.

The changes of IL-6, IL-2, and TNF- $\alpha$  comparison between emergency immunization schedule and routine immunization schedule will be conducted by group (medium-dose group, high-dose group and placebo group) at 7 days after each dose were statistically described, and the difference among groups was analyzed by Rank-sum test.

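### First-dose safety is summarised only by schedule, although the schedules do not differ until day 14, so dose levels are compared after one injection with half the available subjects

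*SAP*

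**What the plan says.** - **Adverse events (6.6.1).** The governing sentence is "AE will be summarised per phase and immunization schedule as follows", followed by "Fisher exact test will be used to test the difference among groups". For individual doses, "AE after every dose will be summarized using the Safety Set for the corresponding dose, respectively". The only step across schedules is a contrast: "AE occurrence will be compared between immunization schedules by group".
- **Laboratory tests (6.6.2).** "Laboratory parameters for emergency immunization schedule and routine immunization schedule in Phase I will be analyzed in the following way": ANOVA among groups, and a t-test between schedules within each group.
- **Inflammatory factors (6.6.4).** The text describes a "comparison between emergency immunization schedule and routine immunization schedule will be conducted by group (medium-dose group, high-dose group and placebo group) at 7 days"; this applies to both injections, with a rank-sum test among groups.
- **Analysis sets (section 5).** FAS, PPS and IPS are defined by schedule. The Safety Set is not named in that statement, and SS1 covers everyone given dose 1: "The first dose of safety set includes all subjects who have completed the first dose of vaccination, which are recorded as SS1".
- **Design (3.1).** The second injection is on day 14 or day 28. In Phase I each schedule has 72 subjects, "with 36 at medium dosage stage which will run-in first, following by 36 at high dosage stage", each stage randomised 2:1 to vaccine or placebo. In Phase II each schedule has 300 subjects, randomised 2:2:1.

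**The concern.** Schedule is a feature of the two-dose regimen. Up to day 14 it has not yet had any effect on treatment: a medium-dose subject on either schedule has had one injection of the same product. A test between schedules on day 3 or day 7 data therefore compares subjects who have been treated alike. The question that can be answered at that point is how medium, high and placebo differ after one injection, and the plan as written answers it twice, each time with half the subjects.

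First-dose reactogenicity is not a side issue in this trial. Section 3.1 makes the move to the high dosage, and then to Phase II, depend on safety over days 0-7 after the first dose. Section 2.2 names the choice of dosage, as well as of schedule, as an aim of Phase II.

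**Working it through.** **1. Are the first-dose data the same in both schedules?**
- Treatment: dose 2 is on day 14 or day 28 (3.1), so treatment is identical before day 14.
- Solicited AEs: days 0-7 after each dose (3.1), so the first-dose window closes before either second injection.
- Phase I blood and urine tests: day 3 in both schedules (Table 1).
- Phase I inflammatory factors: day 7 in both schedules (Table 1).
- Antinuclear antibody is the exception. Table 1 has no common post-baseline time before day 14, so it is left out of this point.

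**2. Group sizes, starting from the SAP's own totals.**
- Phase I, per stage and schedule: 36 × 2/3 = 24 vaccine and 36 × 1/3 = 12 placebo. Two stages give 48 vaccinees per schedule, and 4 × 36 = 144 in all. Both match section 3.3.
- Phase II, per schedule: 300 × 2/5 = 120 per dose and 300 × 1/5 = 60 placebo. Two schedules give 240, 240 and 120, as in section 3.3.
- Combining schedules therefore takes each dose level from 24 to 48 in Phase I and from 120 to 240 in Phase II. Same-stage placebo goes from 12 to 24, and Phase II placebo from 60 to 120.

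**3. Precision.** With no events in n subjects, the two-sided 95% Clopper-Pearson upper limit is 1 − 0.025^(1/n).

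| n | Upper limit |
|---|---|
| 24 | 14.2% |
| 48 | 7.4% |
| 120 | 3.0% |
| 240 | 1.5% |

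**4. Power.** The SAP gives no reaction rates, significance level or power for safety. The rates below are assumptions, and the test is Fisher's exact at a nominal two-sided 5%. Power is the sum of the binomial probabilities of all tables with p ≤ 0.05, without stratification.

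| Comparison | Assumed rates | One schedule | Both schedules |
|---|---|---|---|
| Phase II, medium v high | 10% v 20% | 52% (120 v 120) | 85% (240 v 240) |
| Phase I, vaccine v same-stage placebo | 30% v 10% | 15% (24 v 12) | 43% (48 v 24) |

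**5. Chance of seeing a case.** For a reaction with a true rate of 5%, one Phase I schedule shows at least one case with probability 1 − 0.95^24 = 71%. Both schedules are tabulated, however, so the chance that a case appears in one table or the other is 1 − (0.95^24)² = 1 − 0.95^48 = 91%, exactly as in a combined table. Splitting the table loses no case.

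**The case against.** **By-schedule reporting is appropriate.** Phase II has to choose a schedule as well as a dosage, the randomisation lists are separate (3.2.1), and assignment to schedule is not described as random. This stands as a reason to keep the by-schedule tables and to stratify any combined analysis. It is no reason to omit the combined analysis.

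**Pooling is unplanned, not excluded.** SS1 is not restricted by schedule, the sentence on individual doses does not repeat the split, and the table shells are in an appendix that is not at hand. A reader could also add the counts. This is fair, and it limits the point to what the SAP text states. Adding counts afterwards does not supply a prespecified, stratified comparison.

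**P-values are nominal (6.7).** True, so the power figures are illustrative. The loss of precision does not depend on testing. Section 6.6.1 plans no intervals for AE rates, so the zero-event limits measure information and do not reproduce a planned output.

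Three stronger readings are tempting, and the document does not support them:
- *Escalation is decided on half the data.* Sections 3.1 and 6.10 do not say whether the DMC sees data by schedule or combined. The effect on those reviews arises only if they follow the layout of 6.6.1.
- *Uncommon reactions are more likely to go unseen.* Step 5 of the working shows otherwise, and AEs and SAEs are also listed.
- *Phase I power for medium v high would double.* Unstratified figures of 31% (24 v 24) and 61% (48 v 48) for 10% v 30% can be computed. But medium and high are enrolled in successive stages and are not randomised against each other, so an analysis that respects stage cannot make that comparison.

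**Conclusion.** The point holds as a loss of precision and power in the first-dose comparison of dose levels. The number of vaccinees per dose level is halved in both phases; this follows from the allocation and needs no assumption. The zero-event limit is about twice as high as it need be in each phase. The power losses (85% to 52%, and 43% to 15%) rest on the assumed rates and a nominal 5% level, and a schedule-stratified test would give somewhat different values. Combining the schedules also assumes that a first injection acts alike in the two cohorts, which the identical treatment makes reasonable and which the retained by-schedule tables allow to be checked.

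The consequence for the DMC reviews is conditional and should be settled by stating what the DMC is shown. The change is worth making because it is nearly free. The by-schedule analysis is not invalid.

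**What to change.** Add to 6.6.1, 6.6.2 and 6.6.4 a first-dose analysis on SS1 by dose group within phase, combining both schedules:
- **Data:** solicited AEs on days 0-7 in both phases; day 3 laboratory tests and day 7 inflammatory factors in Phase I.
- **Phase II:** compare medium, high and placebo with a test stratified by schedule.
- **Phase I:** compare each dose with placebo from its own stage, stratified by schedule. Present medium v high descriptively, as a non-randomised comparison across stages.
- **Keep** the by-schedule tables for dose 2 and for the whole regimen.
- **Section 6.10:** use the combined first-dose table in the Phase I safety interim analysis, and state that this is the version the DMC receives.

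The cost is SAP wording and one extra set of tables, with no new subjects, visits or samples.

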Safety Observation: The immediate reactions occur within 30 minutes after each dose of vaccination will be observed on site. The local and systemic solicited adverse events (AEs) occur within 0~7 days after each dose vaccination, as well as the unsolicited AEs from the beginning of the vaccination to 28 days after the whole schedule vaccination will be collected. Additionally, the SAEs from the beginning of the vaccination until 6 months after the whole schedule vaccination will be collected. Besides, venous blood and urine sample will be collected from all subjects in phase I at different time points before and after vaccination for the blood routine, blood chemistry, urine routine testing, and the testing of serum inflammatory factor and antinuclear antibody, to evaluate the safety; venous blood will be collected from all subjects in phase II at different time points before and after vaccination for the antinuclear antibody. In the safety observation, blood and urine collection at each time point are shown in Table 1.

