#### 4.2.3 Safety Endpoint

The safety endpoints of emergency immunization schedule and routine immunization schedule were as follows:

- (1) Adverse events includes:
  - Solicited adverse events: the systemic adverse events and local adverse events actively collected during the solicitation period (within 0-7 days after each dose of vaccination). Systemic adverse events include fever (axillary), acute allergic reaction, skin and mucosa abnormality, diarrhea, anorexia, vomiting, nausea, muscle pain, headache, cough, fatigue; local adverse events includes pain, induration, swelling, redness, rash, and pruritus.
  - Unsolicited adverse events: Including other adverse events in the solicitation period and all adverse events in the unsolicitation period.
- (2) Serious adverse event (SAE);
- (3) Antinuclear antibody: The positive rates at 28, 42 days after the first dose of vaccination (emergency immunization schedule), and 56 days after the first dose of vaccination (routine immunization schedule). Positive was defined as antinuclear antibody concentration  $\geq 10\text{U/ml}$ .

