### 6.6.3 Antinuclear Antibody

(1) The statistical method for antinuclear antibody evaluation for emergency immunization schedule and routine immunization schedule in Phase I will be carried out as follows.

The positive rate of antinuclear antibody was calculated by group on the 7th day after the first dose of immunization in phase I emergency immunization schedule, and their confidence intervals will be estimated by the Clopper-Pearson method. A Chi-square test or Fisher exact test will be used to detect differences among groups. Furthermore, if statistically significance exists, the pairwise comparison will be conducted between groups by Chi-square test or Fisher exact test.

Descriptive statistics in each group for the antinuclear antibody geometric mean titers (GMTs) and geometric mean increasements (GMIs) at 7th day after the first dose of immunization in phase I emergency immunization schedule, including geometric mean and 95% confidence interval (95% CI), will be provided by group. ANOVA model with log-transformation (per GMT and GMI as above) will be used to detect the difference among groups.

The statistical analysis method of antinuclear antibody evaluation on 14, 21, 28, 42 days after the first dose immunization of phase I emergency immunization schedule and 28, 35, 42, 56 days after the first dose immunization of phase I routine immunization schedule was the same as that of 7 days after the first dose in emergency immunization schedule of phase I.

Additionally, using the same method, the positive rate of antinuclear antibody comparison between emergency immunization schedule and routine immunization schedule in Phase I will be conducted by group (medium-dose group and high-dose group) at 14 days and 28 days after the whole schedule vaccination, respectively. 14 days after the whole schedule vaccination is 28 days after their first dose in emergency immunization schedule and 42 days after the first dose in routine immunization schedule, respectively. Meanwhile, 28 days after the whole schedule vaccination is 42 days after their first dose in emergency immunization schedule and 56 days after the first dose in routine immunization schedule, respectively.

(2) The statistical method for antinuclear antibody evaluation for emergency immunization schedule and routine immunization schedule in Phase II will be carried out as follows.

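### The SAP compares adverse event proportions between schedules although unsolicited events are collected over 42 days in one and 56 days in the other, which biases the routine schedule upward in expectation

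*SAP*

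**What the plan says.** - **Collection window.** SAP section 3.1 (Safety Observation) states that "the unsolicited AEs from the beginning of the vaccination to 28 days after the whole schedule vaccination will be collected".
- **Schedules.** For Phase II, section 3.1 gives the "emergency immunization schedule of day 0,14 or routine immunization schedule of day 0,28, with 300 subjects for each immunization schedule". Each schedule is randomised 2:2:1 to medium dosage, high dosage or placebo.
- **Day mapping.** Section 6.6.3 notes: "28 days after the whole schedule vaccination is 42 days after their first dose in emergency immunization schedule and 56 days after the first dose"; the second figure refers to the routine schedule.
- **AE measure.** Section 6.6.1: "The counts and proportion for AE, related AE, and unrelated AE will be summarised".
- **Per-dose summary.** Section 6.6.1: "AE after every dose will be summarized using the Safety Set for the corresponding dose, respectively". No number of days after each dose is fixed for unsolicited events.
- **Comparison at issue.** Section 6.6.1: "AE occurrence will be compared between immunization schedules by group". In that section AE means any treatment-emergent event, so unsolicited events are included.
- **Solicited events.** Section 4.2.3 has these "actively collected during the solicitation period (within 0-7 days after each dose of vaccination"), so their window is the same in both schedules. Section 4.1.3 says the same for Phase I.

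**The concern.** A proportion of subjects with at least one event grows with the time over which events can be counted. If one schedule is watched for 42 days and the other for 56, ordinary background illness gives the second a higher expected proportion even when the vaccine behaves identically in both.

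The other between-schedule safety comparisons are tied to time since a dose: antinuclear antibody at 14 and 28 days after the last dose (section 6.6.3), inflammatory factors at 7 days after each dose (section 6.6.4). The AE comparison has no such anchor.

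It matters because section 2.2 makes the choice of schedule, on safety and immunogenicity, a purpose of Phase II. Section 6.10 also places the Phase II safety interim at 28 days after the last dose, the point at which follow-up is 42 days in one schedule and 56 in the other.

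**Working it through.** **Step 1: window lengths.** Inputs are the second-dose days (14 and 28) and the 28 days of collection after it (section 3.1).

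- Emergency: 14 + 28 = 42 days.
- Routine: 28 + 28 = 56 days.

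This reproduces the day 42 / day 56 mapping in section 6.6.3. The ratio is 56/42 = 1.33.

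**Step 2: where the extra days lie.** After dose 2 both schedules have 28 days. The additional 28 − 14 = 14 days all fall between the two doses of the routine schedule. If events are assigned to dose 1 until dose 2 is given, which the SAP does not state, the dose 1 window is 14 against 28 days, a ratio of 2.0.

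**Step 3: effect on the proportion.** The SAP gives no background rate, so 5%, 10%, 20% and 30% over 42 days are assumed, with a constant hazard and no schedule effect. The proportion over t days is 1 − (1 − p42)^(t/42). For p42 = 20% and t = 56: 1 − 0.80^(56/42) = 25.7%.

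| Assumed 42-day proportion | Over 56 days | Risk ratio | Dose 1: 14 days | Dose 1: 28 days |
|---|---|---|---|---|
| 5% | 6.6% | 1.32 | 1.7% | 3.4% |
| 10% | 13.1% | 1.31 | 3.5% | 6.8% |
| 20% | 25.7% | 1.29 | 7.2% | 13.8% |
| 30% | 37.8% | 1.26 | 11.2% | 21.2% |

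The last two columns depend on the attribution rule in step 2.

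**Step 4: chance of a spurious signal.** Group sizes per schedule in Phase II are 300 × 2/5 = 120 for each vaccine dosage and 300 × 1/5 = 60 for placebo. Section 6.6.1 names Fisher's exact test for comparisons among groups and no test for the between-schedule comparison, so Fisher is assumed. All pairs of counts were enumerated exactly, and the probability of a two-sided p≤0.05 with the routine schedule higher was summed.

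| Assumed 42-day proportion | n = 120, 42 vs 56 days | n = 120, equal windows | n = 60, 42 vs 56 days | n = 60, equal windows |
|---|---|---|---|---|
| 5% | 4.0% | 1.1% | 1.7% | 0.5% |
| 10% | 7.8% | 1.4% | 4.2% | 1.1% |
| 20% | 14.7% | 1.7% | 7.5% | 1.4% |
| 30% | 20.9% | 1.8% | 10.4% | 1.5% |

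With unequal windows, a result in the opposite direction stays below 0.3% throughout, so the error runs one way.

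**Step 5: serious events.** Collection runs to 6 months after the last dose, D194 against D208 in Table 1. The ratio is 208/194 = 1.07, which is minor by comparison.

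**The case against.** The case against has real weight.

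- **Solicited events are not affected.** They are collected over equal windows. Where they dominate the total, the bias in the all-AE proportion is diluted. This stands and limits the point to unsolicited, unrelated and total AEs.
- **Section 6.6.1 has partial safeguards.** It separates related from unrelated AEs and analyses AEs by dose and by time of occurrence. Background events should fall mainly in the unrelated line, and timing tables would show events in the extra days. But none of this is tied to the between-schedule comparison.
- **Each schedule has its own placebo group.** A background difference could show there. No planned contrast uses it as a correction.
- **Section 6.7 makes all p-values nominal** and not a basis for formal inference. That limits the consequence. It also says they describe strength of association, and part of that association would be follow-up length.
- **The size rests on assumed rates.** Reactions clustered soon after each dose would hardly be touched.

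Two stronger readings are tempting. One is that the routine schedule must look worse in every dosage group and in placebo. The bias holds only in expectation: under step 3 the routine proportion is higher in all three groups in about 36%, 52% and 63% of trials at 10%, 20% and 30% background. The other is that 14 against 28 days after dose 1 is a planned window. The SAP fixes no per-dose window for unsolicited events, and does not say that the per-dose summaries are what is compared between schedules.

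**Conclusion.** The point holds for unsolicited, unrelated and total AEs. The window lengths of 42 and 56 days follow directly from the SAP, and section 6.6.1 as written compares proportions across them without adjustment.

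Under a constant background hazard and no schedule effect, the routine proportion is inflated by a factor of 1.26 to 1.32, or 1.6 to 7.8 percentage points, for 42-day proportions of 5% to 30%. The lengths are certain. The size is illustrative, because the background rate, the constant hazard and the choice of Fisher's test for this comparison are assumptions.

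The documents do not support reading this as a flaw in the whole safety comparison: solicited AEs and the 28 days after dose 2 have equal windows. Nor do they say how much weight safety carries in choosing the schedule. The change should be made because the bias has a known direction, touches a stated purpose of Phase II and is cheap to remove.

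**What to change.** In section 6.6.1:

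1. Limit between-schedule comparisons of AE proportions to windows both schedules share: days 0-7 after each dose, the first 14 days after dose 1 and before any second dose, and the 28 days after dose 2.
2. Report whole-period between-schedule comparisons as events per person-day, with a rate ratio and 95% CI.
3. Keep whole-period proportions for comparisons among groups within a schedule.
4. State the rule that assigns an unsolicited event to dose 1 or dose 2, and name the test for the between-schedule comparison.

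The cost is SAP wording and a little programming. The analysis needs only AE onset timing, which section 6.6.1 already uses.

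There are two downsides. Events in the routine schedule's extra 14 days leave the shared-window comparison, though they stay in the person-day rate. And that rate is neutral only if the hazard is roughly constant: if all events clustered just after the doses, equal event numbers would give a routine-to-emergency rate ratio of 42/56 = 0.75. The shared-window results should therefore lead, with the person-day rate beside them.
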